4.5 Response Evaluations

Bone Marrow Evaluation of single agent selinexor during Cycle 1: unless there is evidence of progressive disease by examination of the blood, participants should undergo bone marrow evaluation on day 15 (\pm 2 days). This evaluation must be performed prior to administration of day 15 therapy.

Evaluation of response to Cycle 1: participants should undergo response evaluation between days 42 and 56 of Cycle 1 (with the exception of patients who obtain complete response at Day 15 and elect to continue single agent selinexor and forego fludarabine and cytarabine therapy). Patients may be evaluated earlier if there is evidence of hematopoietic recovery or at discretion of treating physician. In cases with hypocellular marrows (<10% cellularity), repeat bone marrow examinations should be considered when there is evidence of hematopoietic recovery.

4.6 Definitions of Dose-Limiting Toxicities (DLT)

Toxicities will be graded according to the CTCAE Common Terminology Criteria for Adverse Events (CTCAE) version 4.0. DLT is based on non-hematologic toxicities that occur during Cycle 1 and that are deemed to be possibly attributable to selinexor.

4.6.2.1 Non-hematologic DLT (*phase I only*)

- Any Grade 5 event
- Any Grade 4 event that is at least possibly related to selinexor, unless event is clearly and incontrovertibly due to extraneous causes or disease progression

4.6.2.2 Hematologic toxicity (*phase I only*)

Grade 3 or 4 hematologic toxicities will be monitored, but will not be considered dose-limiting toxicities.

4.6.2.3 Dose modifications (See Appendix IV)

During Cycle 1 patients should receive 5 of the 6 intended doses of selinexor; failure to receive 5 doses by Day 35 because of toxicity will be considered a DLT (*phase I only*).

Note that at least 48 hours must pass between doses. Doses should be delayed, rather than omitted, for the following non-hematologic toxicities. Patients should also be treated aggressively with supportive care to reduce toxicities.

Weight loss: if a participant develops Grade 3 weight loss, the next dose of selinexor should be delayed until the weight loss resolves to Grade ≤ 2 . If weight loss does not improve to Grade ≤ 2 within 7 days, this participant will have experienced a DLT (*phase I only*).

Electrolyte abnormalities: if a participant develops Grade ≥ 3 uncorrectable electrolyte abnormalities, the next dose of selinexor should be delayed until the abnormalities resolve to Grade ≤ 2 . If abnormalities do not improve to Grade ≤ 2 within 7 days despite attempts to correct, this participant will have experienced a DLT (*phase I only*).

Infection: the occurrence of Grade 4 infection will not be considered a DLT (*phase I only*). Selinexor should be delayed in any participant with Grade 4 infection or clinical sepsis until condition has clinically stabilized. If during Cycle 1, selinexor is suspended

due to Grade 4 infection or clinical sepsis and participant misses ≥ 3 doses of study drug, the participant will be deemed not evaluable and removed from study. These patients will be replaced during the DLT period, but will be included in the evaluation of the safety profile of the regimen and determining the recommended phase 2 dose (*phase I only*). Selinexor dosing (at the same dose level) can be re-initiated once the patient's condition has stabilized clinically, even when the patient is taking antimicrobial or other agents.

Other DLTs: in the event of a DLT in Cycle 1 (*phase I only*), or other toxicity that warrants discontinuation in the opinion of the investigator, selinexor should be discontinued and the participant removed from study.

The following adverse events will not be considered DLTs (*phase I only*):

- Grade 3 nausea, vomiting or diarrhea (unless persisting > 3 days with appropriate treatment of anti-emetics or anti-diarrheals)
- Alopecia of any grade
- Weight loss of less than 20%
- Electrolyte or serum analyte (e.g., urate) abnormalities that are reversible with standard interventions

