6.3 Response Evaluations

6.3.1 Evaluation of response to Cycle 1 combination therapy

All participants should undergo response evaluation between days 42 and 56 of Cycle 1. In addition to bone marrow aspiration, bone marrow biopsy should be considered to evaluate cellularity. In cases with hypocellular marrows (<10 % cellularity), repeat bone marrow examination should be considered when there is evidence of hematopoietic recovery. If multiple bone marrow examinations are performed after a course of therapy, the last examination will be used to classify the response to that course.

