9.0 OFF-TREATMENT AND OFF-STUDY CRITERIA

9.1 Off-Treatment Criteria

- Development of a DLT
- No response to therapy
- Relapse

- Second malignancy
- Treatment with other antineoplastic therapy or hematopoietic stem cell transplantation
- Development of unacceptable toxicity during treatment
- Refusal of further protocol therapy by participant, parent, or guardian
- Completion of protocol therapy

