9.2 Off-Study Criteria

- Death
- Lost to follow up
- Withdrawal of consent

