Grade 2 (despite maximal anti-diarrheal medication)	Reduce to selinexor to one weekly until resolved to \leq Grade 1, then re-start twice weekly at the current dose level. If diarrhea returns as \geq Grade 2, then reduce selinexor dose by one dose level and dose once weekly until resolved to \leq Grade 1, then re-start twice weekly at reduced dose level
Grade 3/4 (despite maximal anti-diarrheal medication)	Delay selinexor until resolved to \leq Grade 2, then follow guidelines above.
Thrombocytopenia	
Grade 3 Thrombocytopenia Without bleeding	Implement platelet growth factors or transfusions. Begin (or maintain) once weekly dosing at the same dose level until resolved to Grade ≤ 2 .
Grade 4 Thrombocytopenia Without bleeding	Implement platelet growth factors or transfusions. Hold dosing until Grade ≤ 3 and follow above guidelines if Grade 3.
\geq Grade 3 Thrombocytopenia associated with petechiae or purpura	Implement platelet growth factors and/or transfusions. Hold selinexor for 5 days after last bleeding. Restart dosing one dose level below.
Neutropenia	
Grade 3 neutropenia without fever	Implement growth factors.
Grade 4 neutropenia without fever	Implement growth factors. If appropriate, initiate prophylactic anti- microbial agents.
Grade ≥ 3 febrile neutropenia	Implement growth factors. Initiate appropriate broad spectrum anti- microbial agents. Hold selinexor until fever resolves and patient is clinically stable. Restart dosing one dose level below.

Other selinexor-related adverse events	
Grade 1 or 2	Maintain dose level and initiate standard supportive care.
Grade 3	Delay dose until resolved to \leq Grade 1, then reduce by 1 dose level (Table A2.1).
Grade 4	Discontinue selinexor and rule out other causes. If other causes of Grade 4 adverse event are uncovered, selinexor may be re-initiated at 1 dose level reduction (Table A2.1).

All dose modifications should be based on the worst preceding toxicity. Isolated values of \geq Grade 3 alkaline phosphatase values will NOT require dose interruption. Determination of liver vs. bone etiology should be made, and evaluation of gamma-glutamyl transferase (GGT), 5'-nucleotidase (5'NT), or other liver enzymes should be performed. Patients are allowed dose reductions to a minimum dose of 15 mg/m² as described in Table A2.1. a. Common Terminology Criteria for Adverse Events (CTCAE Version 4.03) otherwise specified values.
	

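### Section 4.6.2.3 takes toxicity stops off study while 9.1 and 9.2 do not, and 12.3 does not say how a living patient removed before the response evaluation counts

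*Combined protocol and SAP*

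**What the plan says.** Two sentences in Section 4.6.2.3 end a patient's time on study.

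- **Toxicity.** The sentence opens with a Cycle 1 DLT, tagged phase I only, and continues: "or other toxicity that warrants discontinuation in the opinion of the investigator, selinexor should be discontinued and the participant removed from study". The tag sits on the DLT limb, not on the limb about other toxicity.
- **Infection.** If selinexor is suspended in Cycle 1 for Grade 4 infection or clinical sepsis and three or more doses are missed, "the participant will be deemed not evaluable and removed from study". This sentence has no phase tag. The next one, on replacement and on use in the safety evaluation, is tagged phase I only.

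Elsewhere the protocol treats stopping differently.

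- Section 9.1 (off-treatment) lists "Development of unacceptable toxicity during treatment".
- Section 9.2 (off-study) has three entries: death, loss to follow-up, and "Withdrawal of consent".
- Section 6.3.1 states: "All participants should undergo response evaluation between days 42 and 56 of Cycle 1".
- Section 12.3 defines success as CR, CRi or, for those enrolled with under 5% blasts, MRD negativity by the end of one course. Deaths before that point are failures. Patients who are alive but unassessed are not mentioned.
- The sample-size paragraph of the protocol overview gives Phase II as 28 to 39 evaluable patients. Section 12.1 defines evaluability for toxicity in dose escalation; no section defines it for response.
- Appendix IV, on Grade 4 events, says: "If other causes of Grade 4 adverse event are uncovered, selinexor may be re-initiated at 1 dose level reduction".

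**The concern.** The same Phase II patient is off study under 4.6.2.3 and still on study under 9.1 and 9.2. The difference matters because the response evaluation falls at days 42 to 56, and a patient can be removed before then. A site that follows 4.6.2.3 may not obtain that evaluation; a site that follows 9.1 and 9.2 would.

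Section 12.3 does not settle what happens next. A patient who is alive, removed and unassessed could be counted as a failure, excluded, or replaced so that 28 or 39 evaluable patients remain. In the last two cases the patients left out are selected by toxicity or sepsis, which may well be related to response. The primary response rate and the go/no-go decision could then depend on which section each site follows and on a denominator chosen after the data are seen.

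**Working it through.** **Step 1. Reproduce the stated design.** Inputs from 12.3 and 12.4: continue if there are at least 8 successes in 28; declare the therapy worthy of further study if there are at least 16 in 39; null rate 0.30; alternative 0.50; stated errors 10% and 10%. With X ~ Bin(28, p) and Y ~ Bin(11, p),

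P(declare | p) = Σ from x = 8 to 28 of P(X = x) × P(Y ≥ 16 − x).

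- p = 0.30: 0.0943 (probability of stopping after stage 1: 0.365)
- p = 0.50: 0.9001

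A minimax search over designs returns the same boundaries. The plan's figures are correct and are not in question.

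**Step 2. Effect of excluding and replacing removed patients.** Let d be the share of enrolled patients removed before the response evaluation, q their success probability, and p the rate among all enrolled. The documents give neither d nor q. I assume d of 5%, 10% or 20%, and q of zero, half of p, or p. If removed patients are replaced, the success rate among those counted is

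p_c = (p − d·q) / (1 − d).

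Example at p = 0.30, d = 0.10, q = 0: 0.30 / 0.90 = 0.3333. Putting p_c into the Step 1 formula gives the type I error at a true overall rate of 30%:

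| d | q = 0 | q = 0.15 | q = 0.30 |
|---|---|---|---|
| 5% | p_c 0.3158, error 0.137 | p_c 0.3079, error 0.114 | p_c 0.30, error 0.094 |
| 10% | p_c 0.3333, error 0.196 | p_c 0.3167, error 0.140 | p_c 0.30, error 0.094 |
| 20% | p_c 0.3750, error 0.381 | p_c 0.3375, error 0.212 | p_c 0.30, error 0.094 |

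**Step 3. The alternatives.** If removed patients are followed and their true response is recorded, 0.094 and 0.900 are preserved. If they are not assessed and are counted as failures, the counted rate is p_f = p − d·q. This never exceeds p, so the type I error stays at or below 0.094. The cost is power at a true 50%:

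| d | q = 0 | q = 0.25 | q = 0.50 |
|---|---|---|---|
| 5% | 0.900 | 0.870 | 0.834 |
| 10% | 0.900 | 0.834 | 0.744 |
| 20% | 0.900 | 0.744 | 0.508 |

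For example, d = 0.10 and q = 0.25 give p_f = 0.50 − 0.025 = 0.475, with power 0.834. Continuing to collect the response data is therefore the first choice, and the failure rule covers what is still missing.

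**The case against.** The best defence is that nothing in the plan excludes anyone. Section 12.3 speaks of enrolling 28 patients and 12.4 of 16 successes among the 39, so a patient who never achieves a qualifying response is simply not a success. Section 6.3.1 asks for the evaluation in all participants. This has force: loss of response data is a risk created by the wording, not a stated rule. It does not close the gap. A person removed from study may no longer be treated as a participant, the heading of 6.3.1 refers to combination therapy, and the overview counts evaluable patients. That 12.3 names deaths as failures leaves the status of other unassessed patients open.

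Stronger readings that a reader might draw, and why the documents do not carry them:

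- **Safety data are lost.** Section 6.4 requires a final visit, asks for a visit within 30 days of the last dose after a related adverse event, and recommends assessments at least every 30 days until toxicities resolve or stabilise. Section 11.1 captures adverse events for 30 days after removal from treatment, or until other anti-leukemia therapy. In phase I, infection removals "will be included in the evaluation of the safety profile of the regimen". What remains is small: later follow-up is only recommended, and the 30-day visit in 6.4 covers only related events.
- **The infection sentence certainly governs Phase II.** It fits the phase I toxicity-evaluability rule in 12.1, and only the placement of the tag leaves it open. The later sentence allowing selinexor to be re-initiated can refer to patients who missed fewer than three doses.
- **Appendix IV flatly contradicts 4.6.2.3.** Its restart provision applies when another cause is found, whereas 4.6.2.3 applies to toxicity judged to warrant discontinuation. The two can be read together, though not easily.
- **Removal usually comes before Day 16.** Nothing supports this. Only four selinexor doses (days 1, 3, 8, 10) are scheduled before then, so the infection rule would need three of the four missed.
- **Phase I shows the removal rate.** Section 12.3 reports 18 enrolled and Section 2.1 reports 15 evaluable, but no reasons are given, and phase I covered other diagnoses and dose levels.

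**Conclusion.** The conflict between 4.6.2.3 and 9.1/9.2 on study status is real, and its toxicity limb applies to Phase II as written. Together with the silence of 12.3 and the undefined term evaluable, it leaves the primary denominator open to exclusions selected by toxicity. Whether the infection sentence adds to this in Phase II is unclear.

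The size depends on assumptions. With 5% to 20% removed and replaced, type I error at a true 30% goes from 0.094 to between 0.137 and 0.381 if all would have failed, and to between 0.114 and 0.212 if they respond half as often as patients overall. It does not change if they respond equally often. The calculation takes removals as independent between patients and as fully replaced. The documents do not show that such exclusions will occur or how often. The risk is mainly to the response rate, not to the safety data. The denominator should be fixed in the plan before Phase II results are known.

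**What to change.** 1. Reconcile 4.6.2.3 with 9.1 and 9.2 on study status, so that in Phase II stopping treatment does not by itself end collection of response and adverse-event data. State which phase the infection sentence on non-evaluability covers.
2. In 12.3, state that every enrolled eligible Phase II patient stays in the 28/39 denominator. Anyone without a documented qualifying response by the end of course 1, and before any non-protocol anti-leukemia therapy, counts as a failure. The second condition prevents a response to salvage treatment from being credited to the regimen. Use the same denominator in the overview, or define evaluable there.
3. Reconcile 4.6.2.3 with Appendix IV on re-initiation of selinexor. Which stopping and restart rules apply is the sponsor's clinical decision.

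The cost is a wording amendment. No procedure is added, because 6.3.1 already asks for the evaluation in all participants. The estimated response rate may come out somewhat lower. Power falls if some unassessed patients would have responded, for example to 0.83 with 10% removed at half the overall success rate. Completing the evaluations in item 1 keeps that loss small.

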4.7 Cycle 2 and Subsequent Courses

Participants who have acceptable toxicity (Grade 3 non-hematologic toxicity that has resolved, or stable Grade 1-2 non-hematologic toxicity) and have PR or better response are eligible to receive a second course of therapy. Intrathecal therapy may be given prior to Cycle 2 at the discretion of the treating physician.

4.7.1 Cycle 2 combination therapy

Participants may begin Cycle 2 combination therapy when the absolute neutrophil count (ANC) is $\geq 300/\mu\text{l}$ and rising and the platelet count $\geq 30,000/\mu\text{l}$ and rising.

- Selinexor (40 mg/m²/dose) will be given orally on days 1, 3, 8, 10, 22 and 24 at the same dose that was given in Cycle 1.
- Fludarabine (30 mg/m²/dose IV over 30 minutes daily) on days 15-19
- Cytarabine (2 gram/m²/dose IV over 4 hours daily) will be given on days 15-19

Combination therapy will be limited to a maximum of 2 cycles.

4.7.2 Cycle 2 selinexor single agent therapy

Patients who had at least partial response on Day 15 of Cycle 1 may receive selinexor alone during Cycle 2 after consultation with the Principal Investigator. Participants may begin Cycle 2 (and subsequent) single agent therapy when the absolute neutrophil count (ANC) is $\geq 500/\mu\text{l}$ and rising and the platelet count $\geq 50,000/\mu\text{l}$ and rising.

Patients may continue to receive single agent selinexor as long as there is clinical benefit and no disease progression or unacceptable toxicities.

For patients who achieve complete remission, protocol therapy will be discontinued when a suitable donor has been identified and the patient is ready to proceed to HSCT, or two cycles beyond achieving remission. In general, therapy with selinexor should be discontinued approximately 2 weeks prior to HSCT.

4.8 Supportive Care and Concomitant Therapy

Anorexia and weight loss: Selinexor frequently causes anorexia and weight loss. Thus, participants should be weighed daily while inpatient and at every outpatient visit. High caloric supplements and appetite stimulating agents should be considered in all participants.

Prophylactic treatment to prevent anorexia and nausea during is strongly recommended. An example regimen is outlined below, but exact regimen is at the discretion of the treating institution or physician.

- Ondansetron 0.15 mg/kg/dose TID, starting prior to the first dose of selinexor and continuing for at least 24 hours after the dose (may be continued throughout therapy as needed). Granisetron or other appropriate 5-HT₃ antagonist may be substituted for ondansetron.
- Dexamethasone 5 mg/m²/day x 3 days (given on the day prior to, the day of, and the day after selinexor).
- Olanzapine 1.25 to 2.5 mg daily (may be divided BID), starting one day prior to selinexor. If olanzapine is tolerated, the dose may be increased to 5 mg daily as needed.

Missed doses: a maximum of two doses may be given per week. If the dose was missed for more than 24 hours, the dose will be skipped and the next dose will be taken as per schedule. If the dose was missed within 24 hrs, then it will be replaced. Doses should not be administered in less than 48 hours apart and all missed doses should be documented.

Vomited doses: if a dose is vomited within one hour of ingestion, it will be replaced. If vomiting occurs more than 1 hour after dosing, it will still be considered a complete dose. If a patient missed a full week of dosing for non-study drug related events (e.g., a required medical procedure or an unanticipated personal emergency), the days missed will not be replaced.

Compliance to study medication: will be recorded by study personnel after discussion with the patient and drug accountability. Compliance to study medication will be done by the investigator or delegate and recorded in source documents. The date will be recorded as per study drug schedule. The principal investigator or the designee will account for the number of tablets dispensed against those returned by the patient. Any deviations and missed doses will be recorded in the CRF and drug accountability logs for verification

with the reasons. The investigator/designee will try to ensure complete compliance with the dosing schedule by providing timely instructions to the patients

Antineoplastic therapy: Concurrent cancer therapy, including chemotherapy (other than protocol drugs fludarabine, cytarabine and ITHMA), immunotherapy, or biologic therapy cannot be administered to patients while receiving selinexor.

Radiation therapy: Concurrent radiotherapy is prohibited.

Investigational agents: No other investigational agents may be given while the patient is on protocol therapy.

Growth factors: The routine use of filgrastim (G-CSF, Neupogen®) or other growth factors is discouraged, but may be used in cases of documented infection or sepsis during periods of neutropenia, according to institutional practice.

Conjunctivitis prophylaxis: Dexamethasone or prednisolone ophthalmic solution or artificial tears (e.g., hydroxymethylcellulose, hypromellose, polyvinyl alcohol), 2 drops in each eye every 4 hours while awake, should be used during cytarabine administration and for 24 hours after completion to prevent conjunctival irritation.

Drugs undergoing glutathione conjugation: The primary metabolism of selinexor is inactivation by glucuronidation; conjugation with glutathione is a secondary mode of metabolism. Because acetaminophen is associated with glutathione depletion, patients should not take acetaminophen on days of selinexor administration.

Prophylaxis and treatment of metabolic derangement: Care should be taken to prevent hyperuricemia and hyperphosphatemia in participants with large tumor burdens. Such participants should receive IV hydration at 1500-3000 mL/m²/day before the initiation of therapy, oral phosphate binders, and recombinant urate oxidase or allopurinol as needed.

Prophylaxis for *Pneumocystis jiroveci* pneumonia: All participants should receive prophylaxis for *Pneumocystis jiroveci* pneumonia according to institutional guidelines.

Prophylaxis for fungal infections: Because patients with relapsed leukemia are at high risk for fungal infections, all participants should receive antifungal prophylaxis according to institutional guidelines. Prophylaxis with voriconazole or posaconazole are strongly recommended.

Prophylaxis for bacterial infections: Because patients with relapsed leukemia are also at high risk for bacterial infections, all participants should receive antibiotic prophylaxis according to institutional guidelines. We recommend starting prophylactic antibiotics when the ANC \leq 1000 and falling or predicted to fall and continued until the ANC \geq 100 and rising.

Management of febrile neutropenia: All patients with fever $\geq 38.3^{\circ}\text{C}$ on a single occasion or $\geq 38^{\circ}\text{C}$ on two occasions within 12 hours should be hospitalized and treated immediately with broad spectrum antibiotics according to institutional guidelines.

Prophylactic antiemetic: treatment is recommended prior to the first dose of selinexor, although selinexor does not usually cause high grade nausea or vomiting. 5-HT₃ receptor antagonists, with or without glucocorticoids, appear to be effective at preventing nausea associated with selinexor. Olanzapine or mirtazapine are also effective at reducing nausea. Neurokinin-1 receptor antagonists (e.g., aprepitant) should be considered in case of uncontrolled emesis with standard treatments as described above. Neurokinin-1 receptor antagonists can be given with dexamethasone and 5-HT₃ receptor antagonists. Metoclopramide hydrochloride given prior to meals and dronabinol may be used as well.

Selinexor is infrequently associated with delayed, resistant emesis. Many of the regimens associated with delayed emesis are classified as high-emetic risk, and guidelines recommend the use of an NK1 receptor antagonist (either NK-1 blockers (e.g., aprepitant on days 1 to 3 or fosaprepitant on day 1 only), plus a glucocorticoids on days 1 to 4, along with a 5-HT₃ receptor antagonist (particularly second generation agents) on day 1. This regimen is effective against both acute and delayed emesis.

Conventional antiemetics are more successful at preventing emesis than in preventing nausea, particularly delayed nausea. In adult studies, olanzapine once daily (typically given at night to mitigate sedative effects) was proven effective in both antiemetic and nausea control. It may also be useful for management of breakthrough emesis, and to improve food intake in patients with anorexia. Olanzapine is typically used in children greater than 10 years of age.

Restrictions and precautions:

- Alcohol: Ethanol should be avoided on selinexor dosing days as it may compete for glutathione mediated metabolism.
- Fasting: Patients on selinexor should maintain an adequate diet.
- Medications: Acetaminophen (paracetamol, Tylenol[®]) and products containing acetaminophen should be avoided on days of selinexor administration as it may compete with glutathione mediated metabolism.
- Diet: There are no dietary restrictions on this study. Patients should maintain adequate caloric and fluid intake.

